### C. Preliminary Studies/Progress Report

The contact PI [name] has collected pilot data from both his previous institute Northwestern Medicine, as well as in his current Tulsa lab (OU #IRB 12550). The data demonstrated the feasibility of proposed HD-tDCS technology, showing both anodal (over the ipsilesional primary motor cortex) and cathodal (over the contralateral premotor cortex) HD-tDCS reduced the expression of muscle synergies (Fig. 2). The anodal HD-tDCS reduced the latency of MEP of the damaged corticospinal tract while the cathodal HD-tDCS increase the latency of the MEP of the contralateral cortico-reticulospinal tract. Thus, the previous pilot data support our hypotheses that 1) facilitating the ipsilesional primary motor cortex will improve the function of the damaged corticospinal tract and enhance upper limb movement. 2) inhibiting the contralateral premotor cortex will reduce the maladaptive use of the cortico-reticulospinal tract and reduces the synergy impairment.

[figure not shown]

Fig. 1. Reduced expression of muscle synergies after the targeted HD-tDCS. A1-3 Anodal, C1-2 Cathodal.

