### D. Research Design and Methods (What, When, How, Where)

The statistical analysis of our preliminary data indicated that 40 stroke participants are required to ensure the detection of the significance of our results in a complete trial. We will screen up to 50 patients to ensure we can enroll at least **12 stroke** participants in the first year as the pilot sponsored by OSCTR pilot grant. The participants living around the Oklahoma City area (main site) will be asked to come to:

- OU Physician Neurology Clinic [name] (the primary site).
- College of Allied Health at the University of Oklahoma Health Sciences Center located at [name] (the secondary site)

Baseline standard clinical screens including the Fugl-Meyer Motor Assessment (Upper Extremity Portion) will be conducted prior to any intervention trials.

**Overall Overview of Trial Design.** This **sham-controlled cross-over study design** will include three visits: 1) anodal stimulation targeting ipsilesional hemisphere, 2) cathodal stimulation at the contralesional hemisphere, 3) sham stimulation. The sequence of the stimulations will be **randomized and double-blinded**. After each intervention, there will be a 2-week **wash-out period** (minimum) prior to providing the next intervention in the sequence. Each visit will last up to 3 hours including the preparation time and breaks.

We will use neuro-navigation high-definition tDCS (NNG HD-tDCS) to target specific brain regions in a novel and precise manner. A subject-specific head model will be built to evaluate the effect of lesion size and location on the electrical field of tDCS. The MR images (or CT images) will be used to build these subject-specific head models. The stimulation electrode montage and inter-electrode distance will be carefully examined by computer simulation to determine the optimal setup and dosage for NNG HD-tDCS. Based on our pilot test, the stimulation dosage will be set as 2 mA, 20 min, the dosage for best-influencing neuroplasticity according to the safety guidelines of HD-tDCS(13,14).

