**Assessments and Outcome Measures.** The following assessments will be performed for baseline, pre- and (immediate) post-intervention time frames. The Fugl-Meyer-Upper Extremity (FM-UE) assessment Part A - mainly related to the muscle synergies and serves as the primary outcome measure. This subset FM-UE assessment increases the sensitivity of the measure and reduces the test time from 30 mins (full assessment) to 10 mins. The TMS-evoke motor-evoked potentials (MEP) will be measured to determine the use of the ipsilesional corticospinal and the contralesional cortico-reticulospinal tract, with MEP latency serving as the secondary outcome measure. The single or paired-pulse TMS will be applied at the respective hotspots for the elbow flexor muscle, i.e., Biceps Brachii, over the ipsilesional primary motor cortex (from which the corticospinal tract originates) and contralesional premotor cortex (from which the cortico-reticulospinal tract originates) with reference to the impaired arm. A 3 min 20 channel Resting-state EEG will also compute the *brain symmetry index* (BSI) as the third outcome measure for evaluating the acute effect of HD-tDCS on brain plasticity. The BSI is defined as the mean of the absolute value of the difference in the mean hemispheric amplitude spectrum; values range from 0 (no asymmetry, normal control) to 1 (maximal asymmetry, more impaired brain function). The total three assessments will last for ~33 min (10 mins subset FU-UE assessment, ~10 mins TMS MEP, and 3 mins EEG recording plus 10 mins procedure time), which will be within the effective period of HD-tDCS. Baseline measurement will be performed at the beginning of the study on the first visit. To ensure there is no carry-over effect, we will compare the outcomes of pre-stimulation measurement with the baseline for each visit.

All recorded data will be de-identified for the analysis. Identifiers might be removed, and the de-identified information may be used for future research without additional informed consent from the subject.

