#### **G. Inclusion / Exclusion Criteria**

Stroke participants should have sustained an ischemic unilateral lesion (confirmed by the most recent clinical or radiological reports) at least 3 months prior to participation in this project. The following inclusion criteria will be applied to the stroke participants: 1) Paresis confined to one side, with moderate to severe motor impairment of the upper limb (Fugl-Meyer upper extremity scores of 10-40); 2) Absence of muscle tone abnormalities and motor or sensory impairment in the unimpaired limb; 3) Absence of severe wasting or contracture or significant sensory deficits in the paretic upper limb; 4) Absence of severe cognitive or affective dysfunction that prevents normal communication and understanding of consent or instruction; 5) Absence of severe concurrent medical problems (e.g. cardiorespiratory impairment); 6) Capacity to provide informed consent; 7) Not using a pacemaker, 8) No metal implants in the head 9) No known adverse reaction to TMS and tDCS; 10) Capacity to provide informed consent; 11) Not pregnant.

We are not performing specific assessments since the main goal of our study is to investigate the motor function and movement recovery after stroke. If participants can communicate with the researcher, and understand the procedures well and have the ability to consent, they meet this criterion (5). Stroke participants using a wheelchair or other assistive mobility devices are eligible to participate if they meet the inclusion criteria (1)-(11).

There may be circumstances under which participation may be terminated by the investigator without consent. The examples may include but not limited to:

- The investigator feels that it is in the individual's best interest.
- The individual's condition worsens, or any new condition makes the individual no longer qualified for this study.
- New information becomes available resulting in the individual no longer meeting the inclusion criteria.
- The individual fails to follow study requirements.
- The study is stopped by the sponsor.

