### **J. Risks and Benefits**

The self-adhesive surface electrodes used to record muscle activity (EMG) may produce minor irritation of the skin; there is also the possibility of an allergic reaction to the electrode paste. The possibility of irritation will be minimized by cleaning the skin with alcohol before and after the application of the electrodes. There is a similar possibility of scalp irritation due to a reaction to the use of EEG/tDCS electrodes.

The tDCS may cause transient itching and tingling at the beginning of the delivery of stimulation due to the change of voltage/current as it ramps up to the targeted intensity. However, most people reported that these are very mild and fade quickly. A small number of participants may report moderate fatigue, particularly during, but not after stimulation. Minor scalp skin irritation may occur but will be minimized by screening participants who self-report having sensitive skin (based on the tDCS Safety Screening Tool (TSST)(16)).

If stroke patients participate in this study, possible benefits may include an improved ability to control their paretic arm during movement tasks. Benefits may or may not continue after the research has ended. Possible benefits to others include an enhanced understanding and treatment of movement disturbances following a stroke.

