## **L. Statistical Analysis Plan**

The statistical and power analysis will be led by [name], Assistant Professor of Research in Department of Biostatistics & Epidemiology, Hudson College of Public Health within the University of Oklahoma Health Sciences Center. The obtained preliminary data will refine our power analysis to provide a more precise estimation of sample size for a future full trial. The effect of HD-tDCS is determined by the change in Fugl-Meyer upper extremity Part A score (primary outcome measure), change in Transcranial Magnetic Stimulation (TMS)-Evoke Motor-evoked Potentials (MEP, secondary outcome measures), and change in Brain Symmetry Index (other outcome measures). All statistical analysis was completed using commercial software Statistical Analysis Systems (9.4, SAS, Carey, NC, USA). After checking for and finding no evidence of a non-normal outcome measure distribution, we analyzed the data using generalized estimating equation (GEE) in SAS using PROC GENMOD. The fixed factors are group (anodal, cathodal, sham), time (pre and post intervention), and their interaction, and the random factor is subject ID. This technique uses correlated linear models for each outcome variable (17,18).

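### The only carry-over check compares each visit with the single visit-1 baseline, so it mixes carry-over with time trend and cannot show that carry-over is absent

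*Combined protocol and SAP*

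**What the plan says.** The trial is a three-visit cross-over of anodal, cathodal and sham stimulation in randomised order, with at least 12 participants (Section D). On spacing, Section D says "After each intervention, there will be a 2-week" wash-out. This is a minimum, and no maximum is given.

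On carry-over, the assessments paragraph of Section D says: "To ensure there is no carry-over effect, we will compare the outcomes of pre-stimulation measurement with the baseline for each visit". The sentence before it fixes the reference value: "Baseline measurement will be performed at the beginning of the study on the first visit". No baseline is described for visits 2 and 3 apart from the pre-stimulation measurement itself. No test, margin, pooling rule, split by preceding condition or action on a positive result is given.

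Section L does not mention the check. Its model is described as follows: "The fixed factors are group (anodal, cathodal, sham), time (pre and post intervention), and their interaction, and the random factor is subject ID". Here, time means before and after stimulation within a visit. There is no term for period or for the preceding condition.

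**The concern.** At visit 1 nothing has yet been given, so the comparison with baseline carries no information on carry-over. If the baseline and the visit-1 pre-stimulation score are the same measurement, which the text leaves open, the difference is zero by construction.

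At visits 2 and 3 the difference contains any carry-over together with everything else that has changed since baseline. The assessment has been repeated several times. At least 2 weeks have passed by visit 2 and at least 4 by visit 3. Some recovery is possible, because entry is allowed when the stroke was "at least 3 months prior to participation in this project". On the primary outcome these would tend to point the same way as carry-over, since Section C reports pilot data "showing both anodal (over the ipsilesional primary motor cortex) and cathodal (over the contralateral premotor cortex) HD-tDCS reduced the expression of muscle synergies".

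Two wrong conclusions are open. A time trend could be reported as carry-over and discredit the cross-over design. Or a non-significant difference in 12 people could be reported as proof that there is none. Section L says that the pilot data will refine the power analysis for the full trial, so either error could affect the next design.

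**Working it through.** The plan gives no figure for this check, so there is nothing to reproduce.

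**1. What the check measures (no effect size assumed).** Take the six possible orders as equally represented, which is an assumption because the documents do not state the balance. Let c be the carry-over after each active stimulation.

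- Share with an active stimulation before visit 2: 4/6 = 2/3.
- Share whose immediately preceding condition at visit 3 was active: 4/6 = 2/3.
- Share with any active stimulation before visit 3: 6/6 = 1.
- Mean number of active stimulations before visit 3: 2 × 2/3 = 4/3.

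Expected pre-stimulation minus baseline, averaged over people:

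| Source of change | Visit 2 | Visit 3 |
|---|---|---|
| Carry-over lasting one visit | 2c/3 | 2c/3 |
| Carry-over that persists | 2c/3 | c |
| Carry-over that accumulates | 2c/3 | 4c/3 |
| One-off practice gain g | g | g |
| Steady trend d per visit | d | 2d |

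Setting 2c/3 = g gives c = 1.5g: a practice gain cannot be told from one-visit carry-over. Setting 2c/3 = d and 4c/3 = 2d gives c = 1.5d: a steady trend cannot be told from accumulating carry-over. The expected values are identical, so sample size is irrelevant to this part.

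**2. Precision.** In units of the SD of one person's pre-minus-baseline difference, the 95% half-width is t(0.975, n−1)/√n.

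- n = 12: 2.201/3.464 = 0.64 SD.
- n = 10 (two people lost, an assumption): 2.262/3.162 = 0.72 SD.

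With 12 people, a two-sided 5% paired t test at one visit has 80% power only for a mean shift of 0.89 SD.

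**3. Illustration by simulation.** Assumptions: paired t test at two-sided 0.05 at visits 2 and 3, flagged if either is significant, pooled over people, six orders × 2 people, independent errors. None of these is stated in the documents.

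| True situation | Flagged |
|---|---|
| No carry-over, no drift | 9% |
| No carry-over, drift 0.1 SD per visit | 14% |
| No carry-over, drift 0.25 SD per visit | 40% |
| No carry-over, drift 0.5 SD per visit | about 90% |
| No drift, persisting carry-over 0.5 SD | 42% |
| No drift, persisting carry-over 1.0 SD | about 90% |
| No drift, one-visit carry-over 0.5 SD | 28% (missed in 72%) |

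Drift alone and carry-over alone give similar flag rates.

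**4. The alternative.** Model the visit-2 and visit-3 pre-stimulation scores on preceding condition and period, with baseline as covariate and subject as random effect (F test on 2 and 9 df, used only for this comparison).

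- False alarms stay near 5% with drift of 0, 0.25 or 0.5 SD per visit.
- The half-width for anodal minus sham is about 0.8 to 0.9 SD. For visit 2 alone (4 v 4 people) it is t(0.975, 9) × √(1/4 + 1/4) = 2.262 × 0.707 = 1.60 SD.
- For equal one-visit carry-over it is no more sensitive than the planned check: 20–21% v 28% at 0.5 SD, and 63–65% v 65% at 1.0 SD.
- By visit 3, everyone whose preceding condition was sham has already had an active stimulation. A persisting 1.0 SD effect is therefore estimated as about 0.5 and detected in about 14–17% of trials, against about 90% for the confounded baseline check. The visit-2 contrast alone estimates it at about 1.0.

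**The case against.** The strongest reply is that little depends on the check. A wash-out of at least 2 weeks follows one 20-minute session, and Section D times the roughly 33 minutes of assessments so that they finish in a window "which will be within the effective period of HD-tDCS", which suggests that the sponsor expects a short-lived effect. The primary outcome is change within a visit, the order is randomised, and no decision is attached to the check. All of this stands, and it confines the harm to what may be said about carry-over.

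A reader might infer that the flaw biases the primary comparison of active with sham stimulation. The documents do not support that. A stable residual shift is present both before and after stimulation and cancels in the change, and randomised order tends to balance common trends. Only carry-over that alters the response to the next stimulation would escape, and nothing in the documents shows that this occurs.

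A reader might also take "Benefits may or may not continue after the research has ended" in Section J as evidence that effects outlast the wash-out. It is general risk-and-benefit wording about the time after the study, and says nothing about carry-over between visits.

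The text does not say that people will be pooled, so a look by preceding condition is not ruled out. It is not specified either, and at one visit it would leave 4 people per condition, with a half-width of t(0.975, 3)/√4 = 3.182/2 = 1.59 SD. Finally, the argument that practice and carry-over point the same way is made for the Fugl-Meyer score. The documents give no equivalent basis for the evoked-potential latency or the brain symmetry index, although elapsed time is mixed into those comparisons too.

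**Conclusion.** The concern holds as a limit on the check. Comparing visits 2 and 3 with the visit-1 baseline cannot separate carry-over from practice, recovery and elapsed time, and with 12 people an interval of about ±0.64 SD cannot establish absence. The claim to ensure that there is no carry-over is not supported.

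The confounding needs no assumed effect size; the exact equivalences rest on balanced orders and pooling over people. The flag rates are illustrative only, because the documents give no SD, drift, carry-over size, test or pooling rule. They show what could happen under one reading, and should not be read as the plan's error rates. The documents do not show that carry-over is present. This should be corrected, but it does not call the design or the primary model into question.

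**What to change.** In Section D, change the purpose of the sentence from ensuring absence to assessment. Suggested text:

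> To assess carry-over, pre-stimulation minus baseline will be reported at visits 2 and 3 with 95% confidence intervals, as carry-over plus time trend. A non-significant difference will not be read as absence of carry-over.

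Also state whether the baseline and the visit-1 pre-stimulation score are one measurement or two.

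In Section L, add:

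> As an exploratory analysis separate from the primary GEE model, pre-stimulation scores at visits 2 and 3 will be modelled on preceding condition (anodal, cathodal, sham) and period, with baseline as covariate, subject as random effect and a small-sample degrees-of-freedom method. Anodal-minus-sham and cathodal-minus-sham estimates will be reported with 95% confidence intervals, beside the same contrasts from visit 2 alone.

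The cost is a few sentences, one extra model and the added reporting, on data already collected. The primary model and the visit schedule do not change. The plan should state the downsides. Intervals are wide: about ±0.8 to 0.9 SD, and about ±1.6 SD for visit 2 alone. The model is robust to time trend but assumes that carry-over does not outlast the next visit, so it roughly halves a persisting effect and will usually miss it. That is why the baseline comparison and the visit-2 contrast are kept beside it. No part of this package can prove absence of carry-over at this sample size.

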## **E. Chart Review**

Chart review (including available medical records and MRI/CT) and enrollment will be performed by our study doctor Co-PI [name].

## **F. Banking/Repository/Database**

The recorded data (EEG, MEP and clinical assessments) will be de-identified and stored for future use. These data may be used as preliminary data for a future large R01 grant application. These data may be re-analyzed for data science projects or publications.

The data will be in OU/OUHSC using the Shared Services File Storage Service offered by OU/OUHSC IT. Shared Services File Storage service offers a secure, state-of-the-art clustered storage system for the research team's data and files, similar to typical Windows or Linux file shares. This service features a robust filesystem utilizing high-speed networking for faster access and enables the research team to store and access files from on or off-campus (with VPN) using Windows, Mac OSX, or Unix/Linux operating systems in a secured way.

#### **G. Inclusion / Exclusion Criteria**

Stroke participants should have sustained an ischemic unilateral lesion (confirmed by the most recent clinical or radiological reports) at least 3 months prior to participation in this project. The following inclusion criteria will be applied to the stroke participants: 1) Paresis confined to one side, with moderate to severe motor impairment of the upper limb (Fugl-Meyer upper extremity scores of 10-40); 2) Absence of muscle tone abnormalities and motor or sensory impairment in the unimpaired limb; 3) Absence of severe wasting or contracture or significant sensory deficits in the paretic upper limb; 4) Absence of severe cognitive or affective dysfunction that prevents normal communication and understanding of consent or instruction; 5) Absence of severe concurrent medical problems (e.g. cardiorespiratory impairment); 6) Capacity to provide informed consent; 7) Not using a pacemaker, 8) No metal implants in the head 9) No known adverse reaction to TMS and tDCS; 10) Capacity to provide informed consent; 11) Not pregnant.

We are not performing specific assessments since the main goal of our study is to investigate the motor function and movement recovery after stroke. If participants can communicate with the researcher, and understand the procedures well and have the ability to consent, they meet this criterion (5). Stroke participants using a wheelchair or other assistive mobility devices are eligible to participate if they meet the inclusion criteria (1)-(11).

There may be circumstances under which participation may be terminated by the investigator without consent. The examples may include but not limited to:

- The investigator feels that it is in the individual's best interest.
- The individual's condition worsens, or any new condition makes the individual no longer qualified for this study.
- New information becomes available resulting in the individual no longer meeting the inclusion criteria.
- The individual fails to follow study requirements.
- The study is stopped by the sponsor.

#### **H. Gender/Minority/Pediatric Inclusion for Research**

Women and minorities eligible to participate in our study based on our inclusion criteria will be actively recruited to mimic the gender and race/ethnicity distribution in stroke survivors. The most recent update on Heart Disease and Stroke Statistics from the American Heart Association includes data on the prevalence and incidence of stroke among women and minorities. Both of these statistics vary by age and race/ethnicity but on average indicate a similar prevalence between males and females (2.4 vs 2.9% of Americans  $\geq 18$  y) with similar prevalence within race/ethnicity of non-Hispanic white, black, and Hispanic males and females (2.2 vs 2.8%, 3.9 vs. 4.0% and 2.0 vs 2.6% of Americans  $\geq 18$  y). The incidence of new and recurring attacks across all ages is slightly higher in females compared to males (53.5 vs 46.5% of Americans  $\geq 18$  y). Annual age-adjusted incidence for the first-ever stroke was higher in black individuals than white individuals in data collected from 1993 to 1994, 1999, and 2005 and reflected in the prevalence statistics. In addition, the age-adjusted incidence of first ischemic stroke per 1000 was 0.88 in whites, 1.91 in blacks, and 1.49 in Hispanics according to data from NINDS for 1993 to 1997. Finally, a smaller study in Texas found a higher incidence of ischemic stroke among Mexican-

Americans compared to non-Hispanic white Americans.

Although there is no theoretical basis upon which to assume that gender or race/ethnicity differences will affect movement control following brain injury in the upper limb, we will nonetheless use our quantitative measure of maximum reaching abduction load to evaluate gender and race/ethnicity differences in abnormal joint torque coupling.

The risk of pediatric stroke is approximately 5 per 100,000 children. Our laboratory environment has been designed such that children age 6 and up can have access to our experimental facility. However, the impact of age/development of the nervous system and the timing of brain injury in children is still unclear, which could be very different from the adult stroke. This study focuses on the exploration of our innovations in studying adult stroke survivors, and, therefore, children will not be recruited for the study.

